Reminder notifications. Participants in the intervention arm will be instructed to use the mLab App and the HIV self-test kit at 3 months, 6 months, 9 months, and 12 months after enrollment. Participants will receive a reminder push notification 2 weeks prior to their scheduled test date and 1 week after their scheduled test date.¹³⁸ In the mLab app, if a participant indicates they have received a preliminary positive HIV test using the home HIV test, participants will be directed to another screen on their smartphone directing them to call the study team or the warm line at the NYP or Lurie clinic (depending on geographic location) to receive follow-up confirmatory testing [and if needed, linkage to care]. Participants will be told that this result does not necessarily indicate that they are HIV positive (see false positive in Protection of Human Subjects), that further follow-up testing is needed, and they should contact the clinic or the study team within 24 hours. The mLab team will return the call within normal business hours. The number and nature of calls from participants to the study team (e.g., related to mLab App use, test interpretation, distress at reactive results) will all be recorded and will be reviewed yearly or at a date determined by the DSMB with our DSMB (see letters of support). We will track linkage to follow-up testing and care. Our DSMB will carefully monitor our study activities and data – see Data Safety and Monitoring Plan. **Sound Retention Efforts.** Participants will be asked after study screening what would be the best way for us to remind them of the appointment (voice phone, text, e-mail). Participant retention during the intervention will be enhanced in several ways. First, participants will be compensated for their time to complete the baseline assessment and completing the follow-up assessments. In addition, during the follow-up survey (6 months), participants will be asked to update their locator information. Using these extensive procedures promotes participant attendance at the follow-up visits, which has been shown to be successful in previous trials.^{139, 140} **We have 4 levels of outcomes:** primary, secondary, intermediate, and program evaluation. The survey items are included in the Qualtrics attachment. The primary outcome for Aim 2 / study trial (Uptake of rapid HIV

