Missing Data. Multiple imputation (MI) methods will be applied to address missing values under the missing at random (MAR) assumption (i.e., missingness can be fully accounted for by variables with complete information).¹⁴¹ These analyses will be complemented with assessment of how sensitive the inferences are to the MAR assumptions. Sensitivity analysis will be performed based on selection models for dropout.¹⁴²⁻¹⁴⁴ Intention-to-Treat (ITT) Analysis: All analyses will use the ITT principle,¹⁴⁵ which requires subjects' data to be analyzed as randomized, regardless of whether they used the mLab App or not.

Aim 3: Monitor and analyze paradata to understand the effect of user engagement of the mLab App on improving HIV testing rates and linkage to care.

To understand barriers and/or facilitators of its use, the mLab app will automatically collect paradata for each user interaction throughout the study. This paradata is considered "free" in that it does not require any additional effort from the user.¹⁴⁶ This data will be analyzed for each user, as well as aggregated to understand what component of the intervention lead to behavior change. We will specifically examine who uses the mLab App and how frequently it is used over time.

Methods. We will capitalize on the use of the extant mLab software which is written as a mobile-friendly web application in hypertext markup language (HTML), hypertext preprocessor (PHP), JavaScript, and Python (for computer vision), and integrates with REDCap for backend data storage. On each page of the mLab app, a PHP script logs every user interaction before the page of the application is displayed to the user. Therefore, any event that would refresh or send the user to a new page (e.g., HTML links) initiates an event-driven paradata capture. The PHP script transmits the data to REDCap through the secure REDCap API.

Data Analysis. The primary paradata that will be collected is shown in Table 4. From this data, we will derive the following use data for each session: duration on each page, page progression through the application, time from login to result, number of rapid test pictures previewed before sent for result, and total time prior to logout. We will analyze the data on multiple scales and perspectives: individual-level (i.e. user-level), application-level, page-level, session-level, and how these differ by demographic characteristics, HIV testing history, technology

Table. Paradata Collected for Each mLab Event

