1. Unique Code
2. Page accessed
3. Time stamp
4. Rapid test image
5. Internet browser type
6. Operating system
7. Device

use, and outcomes measures. At the app-level, we will analyze timestamp data including time of day and day of the week that HIV self-testing is performed. We will also analyze the time-to-HIV self-testing result from App login -- a primary indicator of usability. Efficiency is a major construct of the Health-ITUDEM model, the guiding theoretical framework for our study (see Figure 4). Additionally, we will measure the amount in bytes of user data transmitted. Importantly, longitudinal analysis will determine if user-experience changes with repeated use.

The paradata collected from each page will be analyzed to generate a “heatmap” of user-interaction (i.e., the distribution of activity for each link/button). Use of the heatmap will inform user duration on each page of the application user interaction with the HIV prevention content, the contact pages, and the help page. We will explore usability issues with consideration for how many times users accessed help, and what page of the mLab app referred them to the help, implying the need for clarification. Similarly, contact page paradata will be analyzed to determine at what point in the use of the imaging software (the mLab) users initiated contact with the study team and/or the clinic. Specifically, referring pages to the contact page will be analyzed (i.e., do users engage with contact resources only after a diagnosis is provided?). Finally, we will use paradata to understand when users disengage with the mLab app (e.g., logout after received diagnosis, logout prior to diagnosis, session timeout).

Since the mLab App provides an image-based diagnosis of HIV rapid tests, paradata will be used to understand the process of capturing a photograph for analysis. To this end, we will count the number of images previewed prior to submission of a final image for mLab analysis. Within each image, we will perform digital image analysis to determine orientation, luminosity, and major colors within an image – all factors that would indicate successful analysis in mLab. Importantly, this analysis will be used to improve the computer vision algorithm.

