We will analyze difference in the aggregated data by demographic group (age, race, and risk level) to allow us to better understand engagement with the intervention and potential facilitators and barriers to mLab App use. We will evaluate if grouping by HIV status affects these results in any way (e.g., do HIV+ users engage with features differently than HIV- users?). Finally, as a web application, there is potential for slightly varied experiences on different devices or web browsers, and we will evaluate if there are differences in mLab paradata across devices and browsers.

Risks, Benefits & Monitoring

Potential Risks

The risks of participating in this study are:

We will discuss each of these risks below and describe the protection against these risks under “Adequacy of Protection Against Risks.”

General Risks:

1. A risk of taking part in this study is the possibility of a loss of confidentiality or privacy, including that associated with the app on the participants' phone. Loss of privacy means having their personal information shared with individuals outside of the study team who were not supposed to see or know about their information. The study team plans to protect the privacy of participants. Their plans for keeping your information private are described in the Privacy section of Protection Against Risk.

Risks Specific to the Use of OraQuick:

1. **Subjects must follow package instructions on the OraQuick test and always read the test results from the OraQuick test themselves given that the accuracy of the mLab application has not been proven.** Confirmatory HIV testing is still needed.
2. Participants may mistakenly believe that a negative result of the OraQuick Test means that they are not infected with HIV. There is a chance that the test does not detect an HIV infection. To offset this risk, participants will be repeatedly told that a negative result in the OraQuick test does not mean that they are not HIV infected, since infections that occurred within the prior three months may not be detected by the test, and that condoms should still be worn to avoid the risk of HIV and other STIs.

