Recruitment for study participation will occur following approval by the CUMC IRB. The PI will determine eligibility for inclusion, explain the purpose of the study, answer any questions, and obtain written consent from the participants.

Patients who agree to participate will sign a consent form. Recruitment strategies will be developed in collaboration with clinics and community centers. Potential risks and strategies for risk management will be carefully explained as part of informed consent procedures. All HIPAA requirements will be applied to this study. The study plan, advertisements or recruitment letters, lay description of the study, and all consent forms will be submitted to the IRB following proposal acceptance and prior to study initiation. The study PIs will be responsible for obtaining IRB approval for this study.

We will inform the study participants upon enrollment that the goal of the mLab App is for self-testing and NOT for partner testing/sero-sorting. We will advise participants upon study enrollment and consent that the technology is NOT to be used for their partners during the study. Given this limitation, we will suggest that participants who have partners who are interested in testing should contact the study team for more information on HIV testing.

We will also remind participants that the mLab App is not an approved diagnostic test and recommend seeking confirmatory testing (for both negative and positive test results). Upon receiving a positive HIV test result, study participants will then be directed to another screen on their smartphone with the phone number of the Comprehensive Care Program Warm Line. Participants will be told that this result does not necessarily indicate that they are HIV-positive but that further follow-up testing is needed. Participants will also be advised to contact the Clinic or the study team within 24 hours of receiving a positive test result. The number and nature of calls from participants to the study team (e.g., related to mLab App use, test interpretation, distress at reactive results) will all be recorded. All participants will be advised to test quarterly, and will receive the referral number to the Comprehensive Care Clinic.

b. Protections against Risks

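### Aim 3 reads contact-page views as contact initiated by the user, without setting aside views the app may generate itself, and its HIV+ versus HIV- comparison is confounded by in-app test completion

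*Combined protocol and SAP*

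**What the plan says.** All references are to the combined protocol and SAP.

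- **Aim 3, Data Analysis (contact pages).** The plan says that "contact page paradata will be analyzed to determine at what point in the use of the imaging software (the mLab) users initiated contact", whether to staff or to a clinic, and that "referring pages to the contact page will be analyzed". The question put to these data is "do users engage with contact resources only after a diagnosis is provided".
- **Aim 2, Reminder notifications.** Once a user enters a preliminary positive home result, the plan states that "participants will be directed to another screen on their smartphone directing them to call the study team or the warm line". Recruitment and Informed Consent, under Adequacy of Protection against Risks, describes the same routing: "study participants will then be directed to another screen on their smartphone with the phone number of the Comprehensive Care Program Warm Line".
- **Aim 3, Methods.** On logging, "any event that would refresh or send the user to a new page (e.g., HTML links) initiates an event-driven paradata capture". The table of paradata fields has seven entries. None marks whether a page was opened by the user or by the app, and none is the referring page.
- **Aim 3, Data Analysis (HIV status).** Results will be grouped by HIV status, for example "do HIV+ users engage with features differently than HIV- users".
- **Aim 2, Eligibility criteria and Study Enrollment.** Only people with a non-reactive rapid test at baseline are randomised.
- **Aim 2, Reminder notifications (calls).** The number and nature of participants' calls to the study team are recorded. Aim 3 does not use that record.

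**The concern.** There are two separate faults.

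**What a contact view means.** Opening a page that shows a telephone number is not the same as calling it. The routing adds to this. A positive report moves the user to a call screen, and that move is logged like any other. If the screen is among the contact pages analysed, its referring page is the result step, which is the pattern the plan would read as contact following a diagnosis. The view would reflect how the app is built, not what the user chose.

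**Who is being compared.** HIV+ status found through the app can arise only by testing in the app. HIV- status needs no test after baseline. Any measure tied to the testing workflow (test and result pages, images previewed, progression through pages) will then differ between the groups partly because of how they are formed.

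Aim 3 is meant to show which parts of the app matter for testing and linkage. A descriptive finding that HIV+ users engage more, or that contact follows diagnosis, could be reported as behaviour when some of it is routing or group definition.

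**Working it through.** The plan gives no figure for this point, so there is nothing to reproduce. The first steps set the text side by side; the later ones are an illustration.

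**Step 1. Is a routed view distinguishable as planned?** The trigger is entry of a positive result, which is recorded. Each logged event has a page name and time stamp. Routed loads can therefore probably be recovered by page name plus the recorded positive entry, but no rule in the plan tells the analyst to do so.

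**Step 2. Inputs.** From the documents: 210 users in Aim 3 (Table 1), and about 25-40 positive tests expected (Aim 2, Data Analysis), with no split by arm. Assumptions:

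- Positive reporters in arm 1 number 10-20. This comes from 25 × 210/525 = 10 and 40 × 210/525 = 16, or from 25/2 = 12.5 and 40/2 = 20 if only arms 1 and 2 are meant.
- The voluntary contact-page rate v is 5-50% and is the same in HIV+ and HIV- users.
- Half of voluntary views come after the result, with one view per viewer.
- The routed screen is counted as a contact page.

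**Step 3. Contact-page use by HIV status.** Routing makes all positive reporters viewers, so the gap is 100% − v.

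| v | Gap (points) |
|---|---|
| 5% | 95 |
| 30% | 70 |
| 50% | 50 |

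The plan specifies no test here. Purely to show how decisive the artefact would look, a two-sided Fisher exact test gives p = 0.0017 for 10/10 versus 100/200 (10 positives, v = 50%) and about 7 × 10⁻²¹ for 20/20 versus 10/190 (20 positives, v = 5%). With routed views removed, p lies between 0.51 and 1.0 across the scenarios.

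**Step 4. Share of contact views that fall after the result.**

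- Positive reporters only: (0.5v + 1)/(v + 1). At v = 50% this is 1.25/1.50 = 83%; at v = 5% it is 1.025/1.05 = 98%. The true voluntary share was set at 50%.
- All 210 users, with k positive reporters: (0.5 × 210v + k)/(210v + k). At v = 50%, k = 10: 62.5/115 = 54%. At v = 5%, k = 20: 25.25/30.5 = 83%.

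The all-user figure moves from 50% to 54-83%. It is shifted but not fixed.

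**Step 5. Test completion by HIV status.** Among users found positive through the app, completion of an in-app test is 100% by definition. If a fraction c of HIV- users complete one, the built-in gap is 100% − c. It vanishes only if every HIV- user tests in the app. The documents give no value for c.

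**The case against.** The strongest reply is that the documents never say the call screen is the contact page that Aim 3 analyses. The Aim 1 use cases list a separate function, chosen by the user, for contacting the team with a question, and the app workflow is in attachments not reproduced here. If only that function is analysed, the routing artefact does not arise. This stands, and it is why the routing part is conditional. It does not answer the point that a view is not a contact, nor the test-completion fault.

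It is also fair to say that the field list is described as primary rather than complete, and that a link-level heatmap is planned, so the data needed for a correction may well exist. What is missing is a rule.

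Several stronger readings are tempting but not supported:

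- **A reader might infer that routing alone answers both Aim 3 questions.** It touches only positive reporters and cannot erase earlier voluntary visits. The comparison by HIV status also covers features well beyond contact screens.
- **A reader might infer that the app would be credited with linkage that did not occur.** Linkage is defined in the Aim 2 Data Analysis by attendance at a first HIV care appointment or documented care elsewhere, not by page views.
- **A reader might size the test-completion gap from the 60% planning rate.** That rate is for HIV testing over six months, and the outcome is self-reported without restriction to tests done in the app. It is not in-app completion among HIV- users.
- **A reader might assume the HIV- group includes people who never opened the app.** Table 1 gives 210, but logging is driven by events and the text speaks of users, so this is unclear. The confounding needs only that some HIV- users opened the app and did not test.

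HIV+ users and positive reporters are also not identical sets. False positives are possible, and someone may be diagnosed outside the app.

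**Conclusion.** The concern holds in a limited form. Whichever screen is meant, Aim 3 infers contact from page views, and its HIV-status comparison mixes engagement with having tested in the app. If the routed call screen is also counted, contact-page use and post-result timing are inflated for positive reporters, and the all-user timing result is biased without being determined.

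The 70-95 point gap (voluntary rate 5-30%) and the other figures are illustrative. They rest on assumed voluntary rates, an assumed number of positive reporters and an assumed even split of voluntary views before and after the result. The direction does not depend on those values, provided the routed screen is counted and fewer than all HIV- users open the page.

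These are descriptive analyses. The arm 1 versus arm 2 testing comparison and the linkage outcome are untouched. The change is worth making because it is cheap and because, with few positives, a handful of routed views could settle the description.

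**What to change.** **Contact-page analysis.** State which screens count as contact pages. Identify app-routed loads, preferably by a flag set when the page is logged, otherwise by page name plus the recorded positive entry. Exclude them from the contact-page and referring-page counts or report them separately. Define initiated contact by a user action, such as tapping to call or sending a message, or by the calls already recorded, linked to paradata by participant. The recorded calls are those to the study team; the plan does not say calls to the clinic line are logged, so call records alone may undercount contact.

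**HIV-status comparison.** Compare HIV+ and HIV- users among those with at least one completed in-app test, and report activity before and after result entry separately.

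**Cost.** One log flag or derivation rule, a linkage to records already planned, and a few lines in the analysis plan. No clinical procedure changes. The downside is a smaller, more selected HIV- group, which should be stated when the results are described.

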Arm 1-Intervention Arm (mLab App + HIV home test). Youth randomized to the intervention arm will be provided with the mLab App, 2 OraQuick tests (including the package insert), and a box of condoms to take home at baseline. They will receive 2 more OraQuick tests at their 6 month visit. Participants may come in person to receive their tests or their tests may be mailed to them at their verified address if they are unable to complete the in-person visit. The OraQuick tests will be sent via tracked shipping through USPS, FedEx, and UPS. At their baseline appointment, youth will also be sent an email or text with links to mobile-optimized online prevention information, including PrEP and HIV testing information that is found on the CDC website. They will also receive a study information card listing the Columbia University School of Nursing / Lurie Children's study teams' contact information. The goal of the mLab App is not for partner testing. We will advise participants upon study enrollment and consent (see Protection of Human Subjects) that the technology is NOT to be used for this purpose in this study. Given this limitation, we will suggest that participants who have partners who are interested in testing should contact the study team in each respective city for more information on HIV testing. We will also reinforce with participants that the mLab App is considered a screening device and they should seek confirmatory testing (for both negative and positive test results). The mLab App is mobile app on your phone that is accessible using a login name and password. The app will provide HIV prevention information, push notification reminders for testing, step-by-step instructions for using the OraQuick HIV tests, an image upload function to send an image of your OraQuick HIV test to the study team.

Participants will:

- a) be asked to manually enter the Oraquick test results; and
- b) take a picture of the test results for the app to analyze the results; and

- c) receive the app's interpretation of the Oraquick test results.

By using the app, we are asking participants to help test the app's ability to interpret the results of the OraQuick tests. If you test HIV positive by the OraQuick HIV test and/or the mLab app will provide information on how to set up follow-up confirmatory testing within the following 24 hours. All information that you provide within the app will be stored on a secured server at Vanderbilt University

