mLab Image-Processing Evaluation Methods. During use of the mLab App, participants will submit images of their Oraquick self-test to the app for analysis by an automated image-processing algorithm. Prior to submitting this image for analysis, participants will be asked to interpret the results of the test using the instructions that are provided standard with the OraQuick test. This self-reported result will be recorded and uploaded with the user-submitted image of their rapid test. Study team members with expertise in rapid test use and analysis will evaluate the uploaded images of each rapid test, and provide an additional assessment. The user-submitted result and the study team assessment will not be used by mLab in its automated image-processing. All users that submit tests that are identified as positive, either by the automated image-processing in mLab, the study team personnel's inspection of the image of the rapid test, or by the study participant themselves, will be referred for confirmatory testing.

(*Hypothesis 3*).**mLab Image-Processing Data Analysis Plan.** Including the confirmatory test, which will be treated as the gold standard to determine whether a test result is truly false or positive, there will be results from four analysis methods collected on the same set of tests (1. User-submitted results, 2. Study team interpretation of uploaded images, 3. Automated mLab App results, 4. Confirmatory testing). The sensitivity and specificity for each of these methods will be compared using McNemar's test. This will result in the following statistical comparisons for both sensitivity and specificity: 1) user-submitted analysis to study team analysis, 2) user-submitted analysis to mLab analysis, 3) study team analysis of uploaded images, 4) user-submitted analysis to confirmatory testing, 5) study team analysis to confirmatory testing, 6) mLab analysis to confirmatory testing.

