This study will be submitted to the IRB before starting the study. We will be careful to ensure that no coercion occurs during the recruitment periods by ensuring the voluntary participation of both healthcare providers and patients. All participants will be screened to assess for study eligibility. Non-participation will not affect patients' medical care in any way.

- 1) Confidentiality: The smartphone that is connected to the mLab App will require a password. All study data, including mLab App results will be encrypted and stored on secure HIPAA-compliant servers at the Columbia University Medical Center campus. All study data will be kept in password-protected computers or file cabinets in locked offices. All study data will be maintained in a completely secure and HIPAA-compliant environment. All servers have HIPAA-compliant security. Nonetheless, there is always the risk of a data breach, so we will make our study participants aware of this risk upon enrollment.
- 2) False Negative Results: The mLab App has the potential for providing a false negative result, especially during the period of acute HIV infection in which a newly infected individual may be most contagious.

We will clarify these issues before giving the mLab App to participants, test their understanding of the limitations of the HIV Home Test with a structured instrument (Appendix B), provide a study information card that contains information about test limitations, and recommend use of condoms regardless of the test outcome. Upon enrollment, we will explain to participants that the mLab App cannot determine their status with 100% accuracy. The mLab App may not detect acute HIV infection.

- 3) Risk of receiving a false positive HIV home test result: Participants will be informed of the limitations of the mLab App, including the occurrence of false positive results. Again, the study team will stress the need for confirmatory testing.
- 4) Distress a participant may experience if s/he receives a positive HIV result at home: If a research subject gets a positive result in the mLab App at any point during participation in this study, this result will require confirmation. The study team will provide the participant with a confirmatory test and referrals for treatment and care if needed, including psychological assistance.

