The participant will be referred for follow-up testing and care at a clinic at Columbia University Medical Center or Lurie Children's Hospital. We have clinicians on staff at the clinic who are part of our study team.

We detail below the risks and procedures undertaken to minimize them for the intervention arm.

1. **Participants must follow package instructions on the OraQuick test.** They must always read the test results from the OraQuick test themselves, given that these results are more reliable than the mLab App results and the accuracy of the mLab app results have yet to be proven. Participants will be required to report the results from the manual real and enter it into the mobile app and will be contacted either by phone or by the app's messaging portal. In addition, confirmatory HIV testing will be required if an individual provides positive test results from the manual read of OraQuick.
2. Participants may mistakenly believe that a negative result of the Oraquick Test means that they are not infected with HIV. There is a chance that the test does not detect an HIV infection. To offset this risk, study staff will remind participants upon enrollment that a negative result in the OraQuick test does not mean that they are not HIV infected, since infections that occurred within the prior three months may not be detected by the test, and that condoms should still be worn to avoid the risk of HIV and other STIs. Study staff will ask participants to explain their understanding of the meaning of a negative Oraquick test result.
3. Participants may experience distress if they get a positive result in the OraQuick HIV test. If a participant tests positive, he/she will be referred to a clinic for confirmatory testing without a request. If a participant tests negative, then we will refer only if he/she requests additional testing. If at any point during their participation in this study they request a referral for a confirmatory test, the study team will refer them to an HIV/STI clinic for a confirmatory test and referrals for treatment and care if needed, including psychological assistance. We will assist them in scheduling an appointment for a first consultation.

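### The rules on confirmatory testing can be read to conflict when the participant reads a test negative and the app reads it positive; on one reading this biases the app-versus-user comparison in Hypothesis 3

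*Combined protocol and SAP*

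**What the plan says.** Two places give an app-positive test a clear route to confirmation.

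- **mLab Image-Processing Evaluation Methods:** "All users that submit tests that are identified as positive, either by the automated image-processing in mLab", by the study team's inspection of the image or by the participant, are referred for confirmatory testing.
- **Protections against Risks, item 4:** after a positive app result, "this result will require confirmation", and the team provides the test.

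The later list of risks is introduced by "We detail below the risks and procedures undertaken to minimize them for the intervention arm", and only that arm has the app.

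- **Item 1:** "confirmatory HIV testing will be required if an individual provides positive test results from the manual read of OraQuick".
- **Item 3:** "If a participant tests negative, then we will refer only if he/she requests additional testing".

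Risks Specific to the Use of the mLab App, item 1, makes the manual read the result of record and calls the app's output investigational.

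Other text bears on the same case without settling it.

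- **Reminder notifications:** the follow-up screen opens "if a participant indicates they have received a preliminary positive HIV test using the home HIV test".
- **Arm 1-Intervention Arm:** an incomplete sentence, "and/or the mLab app will provide information on how to set up follow-up confirmatory testing within the following 24 hours", probably extends that information to app positives.
- **Protections against Risks, item 7 (Imaging Algorithm):** staff contact the participant when the manual and app results differ. It does not say that a confirmatory test follows.

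For Hypothesis 3, confirmatory testing is the gold standard: "The sensitivity and specificity for each of these methods will be compared using" McNemar's test.

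**The concern.** Hypothesis 3 expects the app to be more sensitive and more specific than the participant's own read. McNemar's test uses only tests on which the two readers differ, and each such test counts only if its true status is known. The evidence that the app is more sensitive comes from infections that the user missed and the app caught. The evidence against its specificity comes from false alarms raised by the app alone. Both lie in the user-negative, app-positive cell, which is the cell where the referral wording can be read two ways.

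If staff worked from the intervention-arm list, with a negative test taken to mean a negative manual read, that cell would be verified only in part. If none of it were verified, every confirmed infection would be user-positive (user sensitivity 100% by construction) and every confirmed non-infection would be a user false positive (user specificity 0%). There is also a safety side: a participant who misreads a true positive might not be referred.

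**Working it through.** The documents give no sample size, accuracy values or power for Hypothesis 3, so there is no stated figure to reproduce. Every accuracy input below is an assumption, and the two readers' errors are taken as independent given true status.

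Let c be the share of user-negative, app-positive tests that get a confirmatory result anyway. Full uptake of the referral in the image-processing methods gives c = 1. The intervention-arm list, read as above with nobody confirmed by another route, gives c = 0. The true value is unknown.

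**Sensitivity.** Let su be user sensitivity and sa app sensitivity, with sa = 0.95 assumed. The verified share of infected tests is v = su + c(1 − su)sa. The user estimate is su/v and the app estimate is [su·sa + c(1 − su)sa]/v.

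For example, with su = 0.80 and c = 0.5, v = 0.80 + 0.5 × 0.20 × 0.95 = 0.895. The user estimate is 0.80/0.895 = 89.4% and the app estimate is (0.76 + 0.095)/0.895 = 95.5%.

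App minus user, in percentage points:

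| su | c = 1 | c = 0.5 | c = 0 |
|---|---|---|---|
| 0.80 | +15.2 | +6.1 | −5.0 |
| 0.85 | +10.1 | +3.1 | −5.0 |
| 0.90 | +5.0 | +0.3 | −5.0 |
| 0.95 | 0.0 | −2.4 | −5.0 |

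**Power for sensitivity.** The plan expects 25 to 40 positives overall and gives no split by arm. Pro rata, arm 1 would have at most 40 × 210/525 = 16. Exact McNemar p-values when all discordant pairs point one way are 0.25 for 3 pairs, 0.0625 for 5 and 0.031 for 6, so at least six pairs are needed. With 16 infections and c = 1, power is 4.2% at su = 0.80, 1.2% at 0.85 and 0.2% at 0.90. At c = 0 it is zero.

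**Specificity.** Take two equally specific readers, each misreading a share f of T uninfected tests, with f = 0.5% or 1%. User-only false positives follow Bin(T, f(1 − f)). Verified app-only false positives follow Bin(T, c·f(1 − f)). Four values of T were used:

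- 252 = 210 × 0.60 × 2, using the planned 60% testing rate and one test per tester in each 6-month period;
- 504 = 210 × 0.60 × 4, with two tests per period;
- 672 = 840 × 0.80;
- 840 = 210 × 4, every scheduled test.

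Probability that the exact test (p < 0.05) declares the app more specific:

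| T | f | c = 0 | c = 0.5 | c = 1 |
|---|---|---|---|---|
| 252 | 0.5% | 0.2% | 0.1% | <0.1% |
| 252 | 1% | 4.1% | 1.3% | 0.4% |
| 504 | 0.5% | 4.2% | 1.4% | 0.4% |
| 504 | 1% | 38.2% | 6.8% | 1.1% |
| 672 | 0.5% | 12.2% | 3.0% | 0.7% |
| 672 | 1% | 65.4% | 10.4% | 1.2% |
| 840 | 0.5% | 24.3% | 4.9% | 0.9% |
| 840 | 1% | 83.7% | 14.0% | 1.4% |

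**Tests that every reader calls negative.** Neither rule routinely verifies these. With T = 840, f = 1% and c = 1, the verified uninfected tests number 840 × (1 − 0.99²) = 16.7. Each reader is correct on 840 × 0.01 × 0.99 = 8.3 of them. Apparent specificity is about 50%, against a true 99%. The comparison between readers remains fair, but the absolute values do not.

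**The case against.** The strongest reply is that the plan already covers this case, twice and specifically. The image-processing methods name three triggers, and item 4 of the protections requires confirmation of an app positive. Item 3 of the later list is a general sentence in a paragraph on distress. It does not say whose read counts as negative and does not mention the app. Item 1 says when confirmation is required, not that it is required only then. If negative means negative by every reader, the list agrees with the methods. This stands as far as it goes: the conflict depends on one reading, although the result-of-record statement makes that reading natural.

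Safeguards also make c = 0 a boundary case. Study team members assess the uploaded images, and a positive assessment leads to referral. Staff contact participants about discrepancies. The arm 1 description and the consent section advise confirmation of negative as well as positive results, and item 4 of the list offers further testing to everyone. This stands too. These steps raise c by an unknown amount, but none of them states the rule.

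A reader might infer that the plan leaves app positives unconfirmed, or that a false specificity claim is likely. The documents support neither. The high figures need 672 to 840 uploaded tests, no confirmation by any route, and independent errors. A falsely reactive strip would tend to mislead both readers, which produces concordant pairs and shrinks the effect.

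A reader might also expect the rewording to rescue the sensitivity comparison. It would not: referral is not completed confirmation, and power stays very low even at c = 1.

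**Conclusion.** The concern holds in a limited form. The plan gives a clear rule for app positives in two places and wording in a third that can be taken to contradict it. If staff followed the third on that reading, the Hypothesis 3 comparison would be biased against the app on sensitivity and in its favour on specificity, and a misread infection might go unreferred.

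The size cannot be fixed from the documents. Over the assumed range, a false finding of better app specificity occurs in 0.2% to 84% of trials at c = 0 and 0.1% to 14% at c = 0.5. At c = 1 it occurs in at most 1.4%. The number of infections that might be missed is not estimated, because the plan gives neither the split of positives by arm nor the accuracy of users' reads.

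Hypothesis 1, its alpha and its power are unaffected, and app performance is a secondary goal. The wording should be corrected because the remedy is simple and the ambiguous case is the one the app is meant to catch. Separately, under either rule the planned sensitivity and specificity describe only tests with at least one positive read.

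**What to change.** 1. In the intervention-arm list, reword items 1 and 3 so that a positive read by the participant, the app or the study team leads to referral for confirmatory testing. Define a negative test as negative by all three.
2. In Protections against Risks, item 7, state that a user/app discrepancy with either read positive leads to referral for a confirmatory test.
3. Align the screen trigger under Reminder notifications and the incomplete sentence in the arm 1 description, so that any such positive gives the same 24-hour direction.
4. In the Hypothesis 3 analysis plan, state that sensitivity and specificity are conditional on tests positive by at least one reader and are not estimates of absolute accuracy.

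The cost is wording changes and possibly one app trigger. No confirmatory tests are added beyond those the image-processing methods already commit to. At an assumed 1% app false-positive rate, app false positives would number about 840 × 0.01 = 8 among all scheduled arm 1 tests.
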